## 14.6 MISSING CAUSAL RELATIONSHIP TO STUDY DRUG FOR ADVERSE EVENTS

If the causal relationship to the IP is missing for an AE that started on or after the date of the first dose of open-label IP, a causality of yes will be assigned. The imputed values for causal relationship to randomized treatment will be used for the incidence summary; the values will be shown as missing in the data listings.

# 14.7 MISSING DATE INFORMATION FOR ADVERSE EVENTS

The following imputation rules only apply to cases in which the start date for an AE is incomplete (ie, partly missing).

#### Missing month and day

- If the year of the incomplete start date is the same as the year of the first dose of open-label IP, the month and day of the first dose of open-label IP will be assigned to the missing fields.
- If the year of the incomplete start date is before the year of the first dose of open-label IP, *31 Dec* will be assigned to the missing fields.
- If the year of the incomplete start date is after the year of the first dose of open-label IP, *01 Jan* will be assigned to the missing fields.

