# 2.0 INTRODUCTION

This Statistical Analysis Plan (SAP) describes the methodology that will be used to summarize the statistical analyses of the efficacy and safety data for the final protocol of Study RAP-MD-33 (version dated 02MAY2018).

Study RAP-MD-33 is a Phase 3, multicenter, randomized-withdrawal, parallel-group, placebo-controlled, maintenance study to evaluate the efficacy, safety, and tolerability of rapastinel in the prevention of relapse in patients with major depressive disorder (MDD) who completed one of the rapastinel lead-in studies including RAP-MD-30 and RAP-MD-32. The RAP-MD-31 study was terminated before any patient was enrolled. Thus, there is no patient rolled-over from the RAP-MD-31 study to RAP-MD-33 study.

The study will be conducted in the following periods:

- An 8- to 16-week open-label treatment period (OLTP) where patients receive rapastinel 225 or 450 mg IV weekly
- A randomized double-blind treatment period (DBTP) of at most 52 weeks of treatment duration where patients are randomized 1:1:1 to either rapastinel 225 or 450 mg weekly, rapastinel clinically driven schedule (IV, 225 or 450 mg, variable interval, placebo on intervening weeks) or placebo
- A 2-week safety follow-up period

In order for patients to transition from the OLTP and be randomized into the DBTP, the patient must meet the stability criterion sometime after 8 weeks (and up to 16 weeks) during the OLTP. A patient will be considered a stable responder upon achieving both criteria (1) and (2) below:

- 1) An observed Montgomery-Asberg Depression Rating Scale (MADRS) total score  $\leq 12$  with no more than one modest MADRS excursion (MADRS total score > 12 but  $\leq 16$ ) for at least six consecutive weeks.
- 2) An observed MADRS total score  $\leq 12$  for at least two consecutive visits prior to randomization.

The OLTP starts with the first dose of open-label treatment and ends with one of the following: the first dose of double-blind treatment for patients who enter the DBTP or Visit 69/Week 52 End-of-Treatment/Early Termination (ET) assessments for patients who do not enter the DBTP.

The double-blind treatment period starts when the first dose of double-blind treatment is administered and ends when the patient meets relapse criteria, completes 52 weeks of double-blind treatment, or discontinues for other reasons.

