## 9.1 ADVERSE EVENTS

AEs will be coded using the Medical Dictionary for Regulatory Activities.

An AE (classified by preferred term) that occurs during the OLTP or thereafter will be considered a treatment-emergent adverse event (TEAE) if it was not present before the date of the first dose of IP in the lead-in study or was present before the first dose of IP in the lead-in study and increased in severity during the OLTP or thereafter. An AE that becomes serious during the OLTP or thereafter will also be considered as TEAE. If more than 1 AE is reported before the date of the first dose of IP in the lead-in study and coded to the same preferred term, the AE with the greatest severity will be used as the benchmark for comparison with the AEs occurring during the OLTP or thereafter that were also coded to that preferred term. An AE that occurs more than 30 days after the date of the last dose of IP will not be counted as a TEAE.

An AE (classified by preferred term) that occurs during the OLTP of the study will be considered a newly emergent adverse event (NEAE) if the AE was not present before the first dose of IP in the OLTP or it was present before the first dose of IP in the OLTP and increased in severity during the OLTP. An AE that becomes serious during the OLTP will also be considered as NEAE. If more than 1 AE is reported before the first dose of IP in the OLTP and coded to the same preferred term, the AE with the greatest severity will be used as the benchmark for comparison with the AEs occurring during the OLTP that were also coded to that preferred term.

An AE (classified by preferred term) that occurs during the DBTP of the study will be considered a newly emergent adverse event (NEAE) if the AE was not present before the first dose of IP in the DBTP or it was present before the first dose of IP in the DBTP and increased in severity during the DBTP. An AE that becomes serious during the DBTP will also be considered as NEAE. If more than 1 AE is reported before the first dose of IP in the DBTP and coded to the same preferred term, the AE with the greatest severity will be used as the benchmark for comparison with the AEs occurring during the DBTP that were also coded to that preferred term.

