## Missing day only

- If the month and year of the incomplete start date are the same as the month and year of the first dose of open-label IP, the day of the first dose of open-label IP will be assigned to the missing day.
- If either the year of the incomplete start date is before the year of the date of the first dose of open-label IP or if both years are the same, but the month of the incomplete start date is before the month of the date of the first dose of open-label IP, the last day of the month will be assigned to the missing day.
- If either the year of the incomplete start date is after the year of the date of the first dose of open-label IP or if both years are the same, but the month of the incomplete start date is after the month of the date of the first dose of open-label IP, the first day of the month will be assigned to the missing day.

If the stop date is complete and the imputed start date as above is after the stop date, the start date will be imputed by the stop date.

If the start date is completely missing and the stop date is complete, the following algorithm will be used to impute the start date:

- If the stop date is after the date of the first dose of open-label IP, the date of the first dose of open-label IP will be assigned to the missing start date.
- If the stop date is before the date of the first dose of open-label IP, the stop date will be assigned to the missing start date.

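### SAP 14.7 anchors incomplete AE start dates only to the first open-label dose, so some adverse events that began in the double-blind period can be dated before it

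*SAP*

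**What the plan says.** SAP 14.7 compares the known parts of an incomplete AE start date with one reference only, the first dose of open-label IP.

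- Month and day missing, same year as that dose: "the month and day of the first dose of open-label IP will be assigned to the missing fields". In a later year, 1 January of that year is used.
- Day missing, in a month after that dose: "the first day of the month will be assigned to the missing day".
- Start wholly missing, with a complete stop date after that dose: "the date of the first dose of open-label IP will be assigned to the missing start date".

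The stop-date check in the same section can only move an imputed start earlier.

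The period boundary lies elsewhere. SAP 2.0 says: "The double-blind treatment period starts when the first dose of double-blind treatment is administered". That dose comes 8 to 16 weeks after the open-label anchor. SAP 9.1 counts an AE as a DBTP NEAE "if the AE was not present before the first dose of IP in the DBTP", or if it worsened or became serious during the DBTP. TEAEs and NEAEs in the DBTP are then summarized by treatment group.

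The section also disagrees with itself on scope. It opens with "The following imputation rules only apply to cases in which the start date for an AE is incomplete", meaning partly missing, yet ends with a rule for wholly missing start dates.

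**The concern.** The imputation can place a start date before the first double-blind dose when the event began after it. Such an event then looks present before the DBTP. It would be counted under open-label rapastinel and would drop out of the by-arm DBTP NEAE and TEAE counts, unless it worsened or became serious in the DBTP. With only the day missing, the loss falls entirely within the calendar month of the first double-blind dose, soon after randomization.

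Elsewhere the SAP resolves missing AE data cautiously: missing severity on or after the first open-label dose becomes severe (14.5) and missing causality becomes related (14.6). Here, missing data can take an event out of the randomized comparison.

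**Working it through.** The plan gives no figure on this point, so there is none to reproduce. The check applies the SAP 14.7 rules to known dates and then works out the share moved.

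**Worked dates.** Patient A: first open-label dose 15 Mar 2018, first double-blind dose 20 May 2018. Patient B: 20 Nov 2018 and 10 Feb 2019.

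| Patient | True onset | Missing | Imputed start | Dated in |
|---|---|---|---|---|
| A | 28 May 2018 | day | 1 May 2018 | OLTP |
| A | 12 Jun 2018 | day | 1 Jun 2018 | DBTP |
| A | 10 Sep 2018 | day | 1 Sep 2018 | DBTP |
| A | 10 Sep 2018 | month and day | 15 Mar 2018 | OLTP |
| A | 10 Feb 2019 | month and day | 1 Jan 2019 | DBTP |
| A | 10 Sep 2018 | all, later stop date known | 15 Mar 2018 | OLTP |
| B | 3 May 2019 | month and day | 1 Jan 2019 | OLTP |
| B | 3 May 2019 | day | 1 May 2019 | DBTP |

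Three cases move a true DBTP event:

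1. Month and day missing, with onset in the year of the first open-label dose, or in a later year when the first double-blind dose fell after 1 January of that year.
2. Only the day missing, with onset in the calendar month of the first double-blind dose, unless that dose was on the 1st.
3. Start wholly missing, with a stop date in the DBTP.

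**Share moved, fixed exposure.** Assumptions not in the documents: first open-label doses spread evenly over a year, and onset spread evenly over T days of DBTP.

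- Day missing. A month averages 365/12 = 30.4 days. The mean number of exposed days left in the month, counting zero when the dose is on the 1st, is (30.4 − 1)/2 = 14.7. The share is 14.7/T: 14.7/56 = 26%, 14.7/182 = 8%, 14.7/364 = 4%.
- Month and day missing. Case 1 amounts to onset in the same calendar year as the first double-blind dose. The share is 1 − T/(2 × 365): 92%, 75% and 50% for 56, 182 and 364 days.
- Start wholly missing, with a stop date in the DBTP: 100% by rule.

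Simulation of the rules gave the same values: 26/8/4%, 92/75/50% and 100%.

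**Share moved, planning hazards** (Protocol 9.7.10 and SAP 12.0: 19% relapse on placebo and 20% dropout per 26 weeks). For placebo, λ = −ln(0.81 × 0.80)/26 = 0.0167 per week. Mean exposure is (1 − e^(−52λ))/λ = 34.8 weeks = 243 days. At a constant AE rate:

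- Day missing: 14.7/243 = 6%.
- Month and day missing: mean onset is 1/λ − 52e^(−52λ)/(1 − e^(−52λ)) = 22.3 weeks = 156 days, so 1 − 156/365 = 57%.

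At the planned hazard ratio of 0.475, λ = (0.475 × 0.2107 + 0.2231)/26 = 0.0124. The same formulas give 268 days of exposure and mean onset at 163 days, hence 5% and 55%.

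**Front-loaded onset.** If exactly half of all events fell evenly in the first 8 weeks, the day-missing share would be 0.5 × 26% = 13%, because an event after week 8 cannot lie in the month of the first double-blind dose. Simulations that put half of each patient's events in the first 8 weeks of that patient's own DBTP give 17% to a little over 20%, and up to 76% to 80% for month and day missing. They run higher because patients who leave early have all their events early. In one such run the day-missing share was 18.5% at the placebo hazard and 17.1% at hazard ratio 0.475, so the loss could differ slightly by arm.

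**The case against.** A reader might infer that AEs beginning in the DBTP are generally moved into the OLTP. The documents do not support that. With only the day missing, about 80% to 94% of DBTP events stay. With month and day missing, later-year events stay when double-blind dosing had begun by 1 January.

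A reader might also infer that the only randomized safety comparison is lost. SAP 9.1 also tabulates deaths, TESAEs, TEAEs leading to discontinuation and related TEAEs by treatment group. Events that worsen or become serious in the DBTP remain DBTP NEAEs. Nor does the visible text describe withdrawal AEs, so a masked withdrawal effect would be conjecture.

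The open-label anchor is not arbitrary: it matches the SAP 9.1 definitions of OLTP NEAEs and of TESAEs. What is missing is a DBTP rule.

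The strongest objection is practical. Visits are weekly, AEs are asked about at each one (Protocol 9.5.2.1.4), edit checks test completeness (Protocol 9.6.2), and SAEs are reportable within 24 hours (Protocol 9.5.2.2). Dates known only to the year, or not at all, should be rare. The rule is the same in every arm, safety is descriptive, and outputs are limited to an abbreviated CSR (SAP 15.0). This bounds the effect but does not correct the rule: followed as written, it misdates identifiable events.

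Two further points stand. Assignment to period by imputed start date is inferred. And a blanket switch to the double-blind anchor would create the opposite error, discussed under the fix.

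**Conclusion.** The point holds in limited form. SAP 14.7 has no rule tied to the first double-blind dose, although that dose defines the DBTP and its NEAEs. If period follows imputed start date, some true DBTP events with incomplete dates leave the by-arm DBTP NEAE and TEAE counts, subject to the exceptions for worsening and seriousness.

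The shares moved are about 6% (constant AE rate) to about 20% (per-patient front-loading) with the day missing, about 56% to 80% with month and day missing, and 100% with the start wholly missing. They rest on evenly spread calendar starts, the planning hazards and the assumed onset patterns. They are shares of incompletely dated DBTP events, not of all AEs. The proportion of AEs with incomplete dates is not in the documents, so the effect on the arm comparison cannot be sized; it is probably small. The change is still worth making, because a stated rule gives a wrong result and the correction is cheap.

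**What to change.** Amend SAP 14.7 as follows.

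- State that AEs are assigned to a period by start date, imputed where necessary.
- For randomized patients, apply a double-blind rule when three conditions all hold: the known date parts allow DBTP onset; the stop date is not before the first double-blind dose; and the AE was not reported at a visit before that dose. Impute the later of the first double-blind dose date and the earliest date compatible with the known parts. Otherwise keep the open-label rule.
- Tabulate DBTP NEAEs under both assignments as a sensitivity check.
- Reconcile the opening sentence, limited to partly missing dates, with the closing rule for wholly missing ones.

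The visible text does not show that the visit of first report is captured, so confirm this before relying on it. There is precedent for a double-blind reference: SAP 14.8.2 imputes medication stop dates against the later of the last open-label and last double-blind doses.

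The cost is a short SAP paragraph, minor programming and one extra table. The new rule keeps every true DBTP event in the DBTP, but some true OLTP events may be counted there. On date parts alone that would be about 18% of day-missing and 88% of month-and-day-missing OLTP events. The stop-date and report-visit checks should lower this, and the same rule applies in every arm.

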## Missing month only

• If only the month is missing, the day will be treated as missing and both the month and the day will be replaced according to the above procedure.

## Missing day only

- If the month and year of the incomplete start date are the same as the month and year of the first dose of open-label IP, the day of the first dose of open-label IP will be assigned to the missing day.
- If either the year of the incomplete start date is before the year of the date of the first dose of open-label IP or if both years are the same, but the month of the incomplete start date is before the month of the date of the first dose of open-label IP, the last day of the month will be assigned to the missing day.
- If either the year of the incomplete start date is after the year of the date of the first dose of open-label IP or if both years are the same, but the month of the incomplete start date is after the month of the date of the first dose of open-label IP, the first day of the month will be assigned to the missing day.

If the stop date is complete and the imputed start date as above is after the stop date, the start date will be imputed by the stop date.

If the start date is completely missing and the stop date is complete, the following algorithm will be used to impute the start date:

- If the stop date is after the date of the first dose of open-label IP, the date of the first dose of open-label IP will be assigned to the missing start date.
- If the stop date is before the date of the first dose of open-label IP, the stop date will be assigned to the missing start date.

#### 14.8 MISSING DATE INFORMATION FOR PRIOR OR CONCOMITANT MEDICATIONS

For prior or concomitant medications, including background ADT, incomplete (i.e. partially missing) start dates and/or stop dates will be imputed. When the start date and the stop date are both incomplete for a patient, the start date will be imputed first.

#### 14.8.1 Incomplete Start Date

The following rules will be applied to impute the missing numeric fields for an incomplete prior or concomitant medication start date. If the stop date is complete (or imputed) and the imputed start date is after the stop date, the start date will be imputed using the stop date.

#### Missing month and day

- If the year of the incomplete start date is the same as the year of the first dose of open-label IP, the month and day of the first dose of open-label IP will be assigned to the missing fields.
- If the year of the incomplete start date is before the year of the first dose of open-label IP, *31 Dec* will be assigned to the missing fields.
- If the year of the incomplete start date is after the year of the first dose of open-label IP, *01 Jan* will be assigned to the missing fields.

## Missing month only

• If only the month is missing, the day will be treated as missing and both the month and the day will be replaced according to the above procedure.

#### Missing day only

- If the month and year of the incomplete start date are the same as the month and year of the first dose of open-label IP, the day of the first dose of open-label IP will be assigned to the missing day.
- If either the year of the incomplete start date is before the year of the date of the first dose of open-label IP or if both years are the same, but the month of the incomplete start date is before the month of the date of the first dose of open-label IP, the last day of the month will be assigned to the missing day.

• If either the year of the incomplete start date is after the year of the date of the first dose of open-label IP or if both years are the same, but the month of the incomplete start date is after the month of the date of the first dose of open-label IP, the first day of the month will be assigned to the missing day.

## 14.8.2 Incomplete Stop Date

The following rules will be applied to impute the missing numeric fields for an incomplete prior or concomitant medication stop date. If the imputed stop date is before the start date (imputed or non-imputed start date), the imputed stop date will be equal to the start date.

## Missing month and day

- If the year of the incomplete stop date is the same as the year of the later of the date of the last dose of open-label IP and the date of last dose of double-blind IP, the month and day of the later of the date of the last dose of open-label IP and the date of last dose of double-blind IP will be assigned to the missing fields.
- If the year of the incomplete stop date is before the year of the later of the date of the last dose of open-label IP and the date of last dose of double-blind IP, *December 31* will be assigned to the missing fields.
- If the year of the incomplete stop date is after the year of the later of the date of the last dose of open-label IP and the date of last dose of double-blind IP, *January 1* will be assigned to the missing fields.

## Missing month only

• If only the month is missing, the day will be treated as missing and both the month and the day will be replaced according to the above procedure.

#### Missing day only

- If the month and year of the incomplete stop date are the same as the month and year of the later of the date of the last dose of open-label IP and the date of last dose of double-blind IP, the day of the later of the date of the last dose of open-label IP and the date of last dose of double-blind IP will be assigned to the missing day.
- If either the year of the incomplete stop date is before the year of the later of the date of the last dose of open-label IP and the date of last dose of double-blind IP or if both years are the same but the month of the incomplete stop date is before the month of the date of the later of the date of the last dose of open-label IP and the date of last dose of double-blind IP, the last day of the month will be assigned to the missing day.

• If either the year of the incomplete stop date is after the year of the date of the later of the date of the last dose of open-label IP and the date of last dose of double-blind IP or if both years are the same but the month of the incomplete stop date is after the month of the later of the date of the last dose of open-label IP and the date of last dose of double-blind IP, the first day of the month will be assigned to the missing day.

# 14.10 ACTUAL TREATMENT FOR ANALYSIS

If a wrong kit was administered to a patient, the treatment to which a patient was randomized will be used for all the analyses.

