#### **9.7.1.3 *Double-Blind Safety Population***

The Double-blind Safety Population will consist of all patients in the randomized patients who received at least 1 dose of double-blind IP.

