#### 4.3 DOUBLE-BLIND SAFETY POPULATION

The Double-blind Safety Population will consist of all patients in the Open-label Safety Population who were randomized to a treatment group during the DBTP of the study and received at least 1 dose of double-blind IP.

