#### 7.0 EXTENT OF EXPOSURE AND TREATMENT COMPLIANCE

#### 7.1 EXTENT OF EXPOSURE

Exposure to open-label rapastinel for the Open-label Safety Population during the OLTP will be summarized for treatment duration, calculated as the number of days from the date of the first dose of open-label rapastinel taken to the date of the last dose taken during the OLTP, inclusive. Descriptive statistics will be presented.

Exposure to double-blind IP for the Double-blind Safety Population during the DBTP will be summarized for treatment duration, calculated as the number of days from the date of the first dose of double-blind IP taken to the date of the last dose taken during the DBTP, inclusive. Descriptive statistics will be presented by treatment group.

The number of IV doses of rapastinel administered to each patient during the OLTP will be summarized using descriptive statistics for the Open-label Safety Population. Similarly, the number of IV doses administered to each patient during the DBTP will be summarized by treatment group, using descriptive statistics for the Double-Blind Safety Population.

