An AE (classified by preferred term) that occurs during the SFU of the study will be considered a newly emergent adverse event (NEAE) if the AE was not present before or at Visit 70 or it was present before or at Visit 70 and increased in severity during the SFU. An AE that becomes serious during the SFU will also be considered as NEAE. If more than 1 AE is reported before or at Visit 70 and coded to the same preferred term, the AE with the greatest severity will be used as the benchmark for comparison with the AEs occurring during the SFU that were also coded to that preferred term.

An AE that occurs more than 30 days after the date of the last dose of IP will not be counted as an NEAE.

An SAE that occurred between the date of the first dose of IP in the OLTP and 30 days after the date of the last dose of IP, inclusive, will be considered a treatment-emergent SAE (e.g., TESAE).

The overall number and percentage of patients with TEAEs, NEAEs, death, TESAEs, TEAEs leading to study discontinuation and TEAEs related to study drug during the OLTP will be tabulated overall, and during the DBTP and the SFU by treatment group.

The incidence of common ( $\geq 2\%$  of patients in any treatment group) TEAEs and NEAEs during the OLTP will be summarized overall by preferred term. Similarly, the incidence of common TEAEs and NEAEs during the DBTP and during the SFU will be summarized by preferred term and treatment group and will be sorted by decreasing frequency starting with the weekly rapastinel group followed by the clinically driven schedule rapastinel group.

Listings will be presented for all patients with AEs and patients who died (if any).

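### SAP 14.10 keeps wrong-kit patients in their randomized arm for the safety and exposure tables as well as for efficacy, so adverse events after a wrongly given dose are counted under the wrong treatment

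*SAP*

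**What the plan says.** SAP 14.10, headed Actual Treatment for Analysis, is a single rule: after a wrong kit, "the treatment to which a patient was randomized will be used for all the analyses". It makes no exception for safety.

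The safety population does not supply one. SAP 4.3 admits patients "who were randomized to a treatment group during the DBTP of the study and received at least 1 dose of double-blind IP", and protocol 9.7.1.3 likewise takes randomized patients "who received at least 1 dose of double-blind IP". Neither says how to group a patient whose treatment differed from the assignment.

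The tables that the rule reaches are in SAP 9.1 and 7.1. Counts of TEAEs, NEAEs, deaths, TESAEs and drug-related TEAEs "will be tabulated overall, and during the DBTP and the SFU by treatment group". Common events "during the DBTP and during the SFU will be summarized by preferred term and treatment group". On exposure, "the number of IV doses administered to each patient during the DBTP will be summarized by treatment group". The visible text of both documents contains no as-treated grouping, no as-treated sensitivity analysis and no listing of wrong-kit administrations.

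**The concern.** Analysis by randomized arm protects the comparison of time to relapse. In a safety table, misclassified treatment usually pulls the arms together, which is not the cautious direction.

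The rule works both ways. A placebo patient who receives rapastinel in error and then has an event adds that event to the placebo column. A rapastinel patient given placebo kits stays in the rapastinel column for time when the drug was not being given. Either way, a true difference between drug and placebo tends to look smaller.

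The opportunity recurs. Under protocol 9.4.4 the IWRS names a kit for each administration, and dosing is weekly for up to 52 weeks. The SAP itself expects that wrong kits may occur, since it writes a rule for them. Without a wrong-kit listing, a reader of the report could not tell that a particular event followed a misallocated dose.

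**Working it through.** The plan gives no figure on this point, so there is none to reproduce. The check is first textual, then a rough sizing on stated assumptions.

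**Does the rule reach safety?** SAP 14.10 covers all analyses. SAP 9.1 and 7.1 tabulate double-blind and follow-up events and dose counts by treatment group. SAP 4.3 and protocol 9.7.1.3 decide who is in the population but not which column a patient sits in. The only visible rule for the column is 14.10, so the consequence follows. Open-label tables are unaffected, because they are presented overall and not by arm.

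**How many placebo injections?** Inputs from SAP 12.0: 200 patients per group, placebo relapse 19% and dropout 20% per 26 weeks. Added assumptions: constant hazards and one injection a week.

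- Combined weekly hazard = −[ln(0.81) + ln(0.80)] / 26 = 0.4339 / 26 = 0.0167.
- Share still on treatment at 52 weeks = (0.81 × 0.80)² = 0.420.
- Mean weeks on treatment = (1 − 0.420) / 0.0167 = about 34.8 (unrounded inputs).
- Placebo-arm injections = 200 × 34.8 = about 6,960.

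**How many wrong kits?** The documents give no rate. If 0.05% to 0.2% of administrations were wrong, the placebo arm would have 6,960 × 0.0005 = 3.5 to 6,960 × 0.002 = 13.9 wrong kits. If every one held rapastinel and each fell on a different patient, 3.5/200 = 1.7% to 13.9/200 = 7% of the arm would be affected. That is a ceiling. If wrong kits were drawn at random from those dispensed, with the three arms dispensing about equally, between one-third and two-thirds would be active: the weekly arm's kits are all active, the placebo arm's are none, and the clinically driven arm's are anywhere between. The count would then be about 3.5 × 1/3 = 1.2 to 13.9 × 2/3 = 9.3.

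**How far would a table move?** The documents give no event rates. Assume 5% on placebo and 15% on rapastinel, and let m placebo patients carry the full rapastinel rate:

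observed placebo rate = [(200 − m) × 5% + m × 15%] / 200

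| m | Placebo rate | Difference (true value 10 points) |
|---|---|---|
| 1 | 5.05% | 9.95 |
| 5 | 5.25% | 9.75 |
| 10 | 5.50% | 9.50 |

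This overstates a single stray dose, because it gives the patient the full rapastinel rate for one injection out of about 35. For common events the shift is negligible. For an event seen once or twice in the trial, one case in the wrong column can change how the table reads.

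**The case against.** The strongest reply is that this is an explicit, prespecified choice with little practical effect. Much of that stands.

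- **The placebo arm is not rapastinel-naive.** Everyone randomized has had 8 to 16 weeks of weekly open-label rapastinel, so one stray dose adds little to what went before. This stands, and a reader should not infer that wrong kits spoil an otherwise drug-free column. What remains is narrower: SAP 9.1 resets the NEAE benchmark at the first double-blind dose, so those tables are meant to show what emerges on double-blind treatment.
- **There is no internal contradiction.** A reader might infer one from the heading of 14.10 or from a safety population whose members "received at least 1 dose of double-blind IP". The documents do not support that. Double-blind product includes placebo, receipt of a dose is only an entry condition, and neither document promises grouping by treatment received.
- **Moving patients could do more harm.** One wrong kit is usually one dose. Transferring the whole patient to a rapastinel arm would carry in events from before the error. This is right, and the remedy must avoid it.
- **Individual cases can be examined.** Patients with events and deaths are listed, injection dates and times are captured (protocol 9.4.11), causality is assessed for each event, and SAEs are reported within 24 hours. This helps, but no visible listing links an event to a wrong kit.
- **Output is descriptive.** SAP 15.0 limits the analyses to those needed for an abbreviated report, and no safety test is visible. This stands. The by-arm tables are nevertheless the safety comparison that readers will use.

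**Conclusion.** The point holds as a minor one. The rule in SAP 14.10 extends analysis by randomized arm to the double-blind and follow-up safety and exposure summaries, where it assigns events to a treatment other than the one given and tends to blur the difference between arms.

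Its size cannot be fixed from the documents. Under the assumptions above, a 10-point difference loses between 0.05 and 0.5 points when 1 to 10 of 200 placebo patients are affected. A reader might take 1.7% to 7% of the placebo arm as an expected figure. It is an upper bound, resting on an undocumented error rate, on every wrong kit being active and on each falling on a different patient. The rule is of practical importance mainly for rare or serious events, or if kit errors are repeated in the same patient or site. If no wrong kits occur, nothing changes. Redacted sections could not be checked for an exception, but the visible wording leaves none.

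**What to change.** 1. Limit SAP 14.10 to the efficacy analyses.
2. For double-blind and follow-up safety and exposure summaries, use treatment actually received, with a rule for mixed kits fixed before unblinding and written for both directions:
   - Events before the first wrong kit stay in the randomized arm.
   - In a placebo-arm patient, events from the first wrong rapastinel dose to 30 days after the last such dose are not counted as placebo events. They are shown separately as post-rapastinel. The 30 days match the cut-off already used for TEAEs and NEAEs in SAP 9.1.
   - Events in rapastinel-arm patients after placebo kits given in error are identified in the same separate display. In the clinically driven arm, a wrong kit is one whose content differs from what the IWRS assigned at that visit.
   - Dose counts follow the content actually given.
3. Add a listing of all wrong-kit administrations, with dates, assigned and given treatment, and the onset of any adverse event relative to the wrong dose.

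The cost is a short SAP change, one derived variable and one listing. The drawback is that a few patients will be presented differently in the safety and efficacy tables, which a footnote can explain.
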